The most recent study on RPWT in KOA was published by Uysal et al. and conducted between 2017 and 2018. This was a single-blind randomized controlled trial including 104 patients aged 50 to 70. Both groups received transcutaneous electrical nerve stimulation for 30 minutes, hot packs for 40 minutes, and a home exercise program for knee muscle strengthening (5 times per week for one month). One group received RPWT (2000 pulses, 10 Hz, 2.0 to 3.0 bar, once per week for three weeks), while the other received sham RPWT (2000 pulses, 10 Hz, 0.1 bar, once per week for three weeks). In both groups, patients were treated with knees flexed at 90°, applying the intervention to sensitive areas or the patellofemoral and tibiofemoral margins. Outcomes included VAS, range of motion, 20-meter walk test, WOMAC, Lequesne disability index, and isokinetic muscle performance, assessed at baseline, post-treatment, 1-month, and 3-month follow-ups. The results demonstrated that RPWT led to superior improvement in all parameters at both 1 and 3 months.²¹

It is worth noting that, based on a literature review conducted for this protocol, no studies evaluating the efficacy of RPWT in Latin American patients with KOA were identified. The present study may be the first clinical trial on RPWT conducted at the Hospital Civil de Guadalajara.

Problem Definition

KOA is one of the leading global health problems. Its management entails high costs and can result in significant disability. RPWT has been shown to be effective in controlling pain and improving function; however, scientific literature on this topic remains limited.

Research question: Is radial RPWT effective when using different application techniques in patients with chronic KOA?

Justification

KOA is a major public health concern worldwide. Its impact is such that in Mexico, KOA limits mobility in 10 out of every 100 adults over the age of 45 and is one of the leading causes of disability overall. The cost of managing KOA is high and increasing exponentially.

OA is among the ten most frequent reasons for consultation in the Physical and Rehabilitation Medicine Department of the “Fray Antonio Alcalde” Civil Hospital of Guadalajara. In 2023, gonarthrosis and other internal knee disorders were the second most prevalent condition treated at the musculoskeletal rehabilitation clinic within the same department.

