RPWT is a non-invasive therapeutic procedure that delivers a single acoustic pulse lasting 1 microsecond to targeted body areas, producing analgesia and promoting healing through a mechanism called mechanotransduction. This mechanotransduction travels through tissues and exerts analgesic, osteogenic, neovascular, and reparative effects. It has been proposed as the main mechanism by which RPWT induces angiogenesis and tissue regeneration at cellular and molecular levels.

Its benefits include analgesia, enhanced protein synthesis, increased vascularization, improved cell proliferation, calcification breakdown, and a protective effect on cartilage and bone.

In OA, RPWT promotes beneficial changes in cartilage and subchondral bone, stimulates chondrocyte activity, and reduces cartilage fissuring. It has anti-inflammatory effects and promotes angiogenesis, helping to relieve pain and improve motor function. RPWT also stimulates meniscal cell proliferation and extracellular matrix repair while modulating central and peripheral sensitization to reduce hypersensitivity and chronic OA-related pain.

RPWT dosing consists of several components that may influence treatment outcomes, including: Frequency (impulses per second), which affects depth and energy distribution (lower frequencies are used for deeper areas; higher for superficial). Number of pulses, with more pulses potentially improving effectiveness but also increasing side effect risks or discomfort. Power, referring to energy per pulse; higher power may be more effective for treating calcifications or dense tissues but may also be more painful. Patient positioning, which may influence effectiveness by improving target orientation and optimizing energy transmission.

Study objectives

General objective: To determine the effectiveness of radial pressure wave therapy (RPWT) using different application techniques in patients with chronic knee osteoarthritis (KOA).

Specific Objectives: 1. To evaluate whether the site of application of RPWT influences clinical outcomes in terms of pain and physical function. 2. To analyze the relationship between the radiographic severity of KOA and clinical outcomes after RPWT. 3. To determine the influence of body mass index (BMI) on clinical outcomes in patients with KOA treated with RPWT.

Materials and methods

Study design: This was a single-blind, randomized controlled trial.

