Sample size calculation: The primary outcome for sample size determination was pain intensity (NPRS). Using a two-tailed α of 0.05, 80% power ($\beta = 0.20$), an expected clinically relevant effect size of 2.0, and a standard deviation of 2.1 (based on prior literature), the required sample size per group was 17 participants. Anticipating a 20% attrition rate, we adjusted the sample to 23 participants per group to preserve statistical power. Therefore, a total of 69 participants were recruited and equally distributed across the three study arms.

Intervention Groups:

- Control group: Patients received 3 weekly RPWT sessions in the supine position with the knee flexed 30°–60°. A total of 2000 shocks per session were applied at the two most painful palpated sites (based on physical examination), using a fixed frequency of 10 Hz and an intensity of 2.0 bar. At the final session, participants were trained to continue with a four-week home-based physical therapy program including superficial thermotherapy, stretching, strengthening, proprioceptive retraining, and general recommendations.
- Experimental group 1: Patients received 3 weekly RPWT sessions in the same position. A total of 2000 shocks were applied to the medial joint line using a non-fixed frequency (10 Hz) and intensity of 2.0 bar. At the final session, they were instructed to follow the same four-week home rehabilitation program as described for the control group.
- Experimental group 2: Patients received 3 weekly RPWT sessions with 2000 total shocks distributed equally over the medial (1000 shocks) and lateral (1000 shocks) joint lines. Frequency was non-fixed (10 Hz), and intensity was 2.0 bar. The same four-week home-based therapy program was prescribed after the third session.

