Blinding: This study will employ a double-blind design. Both participants and the clinical evaluator responsible for conducting the physical and radiographic assessments will be blinded to the group assignments. Participants will be informed that they would receive one of three potential treatment techniques but will not be made aware of the specific approach applied to them. RPWT will be administered by a final-year resident physician in Physical Medicine and Rehabilitation who will be aware of the group allocations but will not be involved in outcome assessments. All data collection and statistical analyses will be conducted by researchers blinded to the group assignments. Furthermore, all treatment sessions will be standardized, with identical instructions, equipment setup, and clinical environments applied across the three groups to minimize performance and detection bias.

Statistical analysis plan

Software: All statistical analyses will be performed using IBM SPSS Statistics version 22.0 (IBM Corp., Armonk, NY, USA).

Descriptive statistics: Descriptive statistics will be computed for all variables. Categorical variables will be reported as frequencies and percentages, while continuous variables will be reported as means and standard deviations or medians and interquartile ranges, depending on their distribution.

Normality testing: The distribution of continuous variables will be assessed using the Kolmogorov–Smirnov test.

Primary outcome: Pain intensity, assessed using the Numerical Pain Rating Scale (NPRS), is defined as the primary outcome.

Secondary outcome: Self-reported physical function, measured with the Western Ontario and McMaster Universities Osteoarthritis Index (WOMAC), is defined as the secondary outcome.

Within-group analysis: To evaluate changes over time within each treatment group (baseline, 2-month, and 4-month assessments), the following tests will be used:

- Paired-samples t-tests for normally distributed data.
- Wilcoxon signed-rank tests for non-normal distributions.
- Bonferroni correction will be applied to adjust for multiple comparisons, when appropriate.

Between-group analysis and interaction Effects: A two-way mixed-design repeated-measures ANOVA will be used to assess:

- The main effect of time.
- The main effect of the group (three levels: pain-site guided therapy, standardized medial line application, and standardized medial + lateral lines application).
- The interaction effect of time × group.

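### The general objective and research question ask whether RPWT is effective, but every arm receives RPWT and the same home programme, so the trial can only compare application techniques

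*Combined protocol and SAP*

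**What the plan says.** All references are to the combined protocol and SAP.

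- **Study objectives, general objective:** "To determine the effectiveness of radial pressure wave therapy (RPWT) using different application techniques", the population being people with chronic knee osteoarthritis. No comparator is named.
- **Problem Definition, research question:** "Is radial RPWT effective when using different application techniques in patients with chronic KOA".
- **Study objectives, specific objective 1:** "To evaluate whether the site of application of RPWT influences clinical outcomes in terms of pain and physical function". This one is comparative, and so is the title.
- **Intervention Groups:** the control arm is itself RPWT: "Control group: Patients received 3 weekly RPWT sessions in the supine position with the knee flexed 30°–60" degrees, with 2000 shocks per session to the two most painful sites. For the medial-line arm, "Experimental group 1: Patients received 3 weekly RPWT sessions in the same position". For the two-line arm, "Experimental group 2: Patients received 3 weekly RPWT sessions with 2000 total shocks distributed equally over the medial (1000 shocks) and lateral (1000 shocks) joint" (quote cut before its last word). All three use 2.0 bar and a stated 10 Hz. Each arm is then given the same home programme of heat, stretching, strengthening and proprioceptive work; for the two-line arm the text reads "The same four-week home-based therapy program was prescribed after the third session".
- **Statistical analysis plan, Within-group analysis:** change over baseline, two months and four months is tested in each arm ("Paired-samples t-tests for normally distributed data", otherwise Wilcoxon), with Bonferroni where appropriate.
- **Statistical analysis plan, Between-group analysis:** a mixed-design ANOVA gives main effects of time and group and their interaction. The group factor has three levels, all of them RPWT.

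**The concern.** Whether a treatment is effective is a question about outcomes with it against outcomes without it. No arm here goes without RPWT: there is no sham arm, no arm with the home programme alone and no untreated arm. A contrast between arms can show that one technique does better than another. It says nothing about how any of them compares with not giving RPWT.

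That leaves the paired tests and the main effect of time as the only planned analyses that could be offered in answer to the general objective. Both measure change from baseline, which mixes any RPWT effect with the home programme, regression to the mean, natural course and placebo response. The Background section itself reports that exercise is about as effective as oral analgesics in this disease, so some improvement from the home programme is to be expected on the protocol's own terms.

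At stake is the headline conclusion. The general objective invites an absolute claim, and no section says that change within an arm must not be used to support one.

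**Working it through.** **1. What the trial is sized for.** Inputs from Sample size calculation: difference 2.0 NPRS points, SD 2.1, two-sided alpha 0.05, power 80%, attrition 20%. For two independent means,

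n per arm = 2 × [SD × (1.960 + 0.842) / difference]² = 2 × [2.1 × 2.802 / 2.0]² ≈ 17.3.

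The plan states 17; rounding up gives 18. Then 18 / 0.8 = 22.5, which rounds up to the stated 23, and 3 × 23 = 69. The stated figures are reproduced to within one patient, and the formula that fits is a comparison of two arms. The sample size therefore addresses a difference between active techniques, not RPWT against its absence.

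**2. What each analysis can identify.**

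| Planned analysis | Comparator | Question it can answer |
|---|---|---|
| Group and time × group terms, Tukey tests | Another RPWT technique | Do techniques differ? |
| Paired tests within an arm | The same patients at baseline | Did scores change, for whatever reason? |
| Main effect of time | The same patients at baseline | Did scores change, for whatever reason? |

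The two- and four-month visits both fall after the four-week home programme. Outcome measures also schedules an assessment straight after the third session, before that programme can act. The within-group list in the SAP omits it, and it too would lack a control.

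**3. How often a within-arm test would be significant with no RPWT effect.** The documents give neither the non-specific fall nor the correlation between visits, so both are assumed and varied. SD 2.1 is the plan's figure, taken here as the SD at each visit. Eighteen per arm is the unrounded requirement of step 1 rounded up.

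- SD of change = 2.1 × √[2 × (1 − correlation)]. At correlation 0.5 this is 2.1.
- Noncentrality = fall × √18 / 2.1.
- Critical t on 17 degrees of freedom: 2.110 at alpha 0.05, and 2.655 at 0.05 / 3 = 0.0167 (three pairs of visits).

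| Assumed fall (points) | Noncentrality | Significant at 0.05 | Significant at 0.0167 |
|---|---|---|---|
| 0.5 | 1.01 | 16% | 7% |
| 1.0 | 2.02 | 48% | 29% |
| 1.5 | 3.03 | 81% | 65% |
| 2.0 | 4.04 | 97% | 90% |

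At a 1.5-point fall, correlation 0.3 (SD of change 2.48) gives 68% and correlation 0.7 (SD of change 1.63) gives 96% at alpha 0.05. With the full 23 per arm and correlation 0.5, the four falls give 19%, 59%, 91% and 99% at alpha 0.05.

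Bonferroni lowers these probabilities. It does not address the problem, which is bias from a missing comparator and not multiplicity.

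**The case against.** The comparative question is already in place. The title announces a comparison of two standardised techniques with pain-site guided therapy, specific objective 1 asks about application site, the sample size fits a two-arm difference, and the ANOVA has group and time × group terms with Tukey tests. The general objective carries a qualifier about different techniques. All of this stands, and a reader who inferred that the trial cannot meet any of its aims would be wrong. The mismatch is confined to the absolute wording, but that wording is in both the general objective and the research question.

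A reader might also infer that the SAP intends within-arm significance as proof that RPWT works, or plans to compare which arms reach significance. The documents do not support either reading. The SAP says only that the paired tests evaluate change over time, and it compares arms by ANOVA. The gap is that no limit is placed on interpretation.

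It can be argued that efficacy is taken as given and only technique is open. The Background describes two sham-controlled trials: one found benefit only in WOMAC pain and some algometric measures, the other on all parameters at one and three months. Problem Definition says RPWT has been shown to be effective. However, Justification calls the evidence inconclusive, so the protocol does not treat the question as settled, and this design cannot settle it.

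Finally, the probabilities depend on the assumed fall. At 0.5 points a significant result is unlikely (16%), and at 1.0 point it is close to even (48%).

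**Conclusion.** The point holds for absolute effectiveness only. With active RPWT and the same home programme in all three arms, the trial can say whether techniques differ. It cannot say whether RPWT works against sham or no RPWT, and neither the within-arm tests nor the main effect of time can fill that gap. This conclusion follows from the design and needs no numerical assumption.

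The size of the risk does need assumptions. With no RPWT effect, SD 2.1, correlation 0.5 and 18 per arm, the chance of a significant paired test in one arm runs from 16% to 97% as the non-specific fall goes from 0.5 to 2.0 points (7% to 90% with Bonferroni). It would go too far to say that a significant change is bound to appear. At falls of 1.5 points or more it is the probable result; at smaller falls it may well not be.

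**What to change.** 1. Reword the general objective and the research question to ask whether pain and function differ between the three application techniques.
2. State in the objectives and the SAP that the trial cannot conclude that RPWT works against sham or no RPWT.
3. Label within-arm change and the main effect of time as descriptive, reported as mean change with a 95% confidence interval, and not as evidence of efficacy. The paired tests need not be deleted if they carry that label.
4. Base conclusions on the group and time × group contrasts. Add that a non-significant contrast does not show that all techniques work or that they are equivalent.

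The cost is wording in the objectives and the SAP. N stays at 69, and treatment and randomisation are untouched. The trial gives up an absolute efficacy claim that its design cannot support.

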Setting and population: Participants with chronic knee osteoarthritis were recruited through a digital campaign and treated at the Department of Physical Medicine and Rehabilitation of the Antiguo Hospital Civil de Guadalajara "Fray Antonio Alcalde" during the third quarter of 2024 (July–September).

Inclusion criteria: Male and female patients aged 50–80 years. Clinical diagnosis of KOA according to the American College of Rheumatology criteria. Minimum of six months of knee pain. Anteroposterior and lateral knee radiographs (within the past year).

Exclusion criteria: Previous knee surgery. Inflammatory arthropathy. Active infection. Fibromyalgia. Cancer. Severe vascular insufficiency.

Elimination criteria: Absence from one or more RPWT sessions. Voluntary withdrawal at any time for any reason.

Sampling and randomization: Patients were randomly assigned to one of three groups using a sealed opaque envelope method (also known as "paper-draw bag method"). Each envelope contained the designation of one of the three groups ("Experimental Group 1", "Experimental Group 2", or "Control Group"). This simple randomization ensured equal allocation probability and minimized selection bias.

Outcome measures: Sociodemographic data were collected using a standardized internal questionnaire. Pain intensity was assessed using the Numerical Pain Rating Scale (NPRS) at baseline, after the third treatment session, and three months post-baseline. NPRS consists of a 10 cm horizontal line where 0 represents "no pain" and 10 represents "worst imaginable pain." Functionality was measured using the Western Ontario and McMaster Universities Osteoarthritis Index (WOMAC), which evaluates pain (5 items), stiffness (2 items), and physical function (17 items), each scored on a 5-point Likert scale (0 = none, 4 = extreme). Higher scores indicate greater impairment. WOMAC was applied at baseline, after the third session, and three months post-treatment. Radiographic severity of KOA was assessed once using the Kellgren-Lawrence (KL) classification based on weight-bearing anteroposterior knee radiographs. The scale ranges from 0 to 4: 0 = normal; 1 = doubtful; 2 = mild; 3 = moderate; 4 = severe. Outcome evaluations will be conducted at baseline, immediately after the third RPWT session, at the two-month follow-up, and at the four-month follow-up after the first session.

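### Participants are eliminated after randomisation for a missed session or withdrawal, and no as-randomised analysis set or missing-data method is defined, so a completers-only comparison is the likely result

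*Combined protocol and SAP*

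**What the plan says.** Materials and methods lists, apart from the inclusion and exclusion criteria, a third set: "Elimination criteria: Absence from one or more RPWT sessions. Voluntary withdrawal at any time for any reason". Allocation comes first: "Patients were randomly assigned to one of three groups using a sealed opaque envelope method". The sessions to which the absence rule refers are then delivered by arm. The control group's entry under Intervention Groups begins "Patients received 3 weekly RPWT sessions in the supine position with the knee flexed 30°–60", and the two experimental groups also have three weekly sessions. Withdrawal has no time limit, so it can occur up to the four-month assessment.

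Attrition is addressed in one place, the sample size calculation: "Anticipating a 20% attrition rate, we adjusted the sample to 23 participants per group to preserve statistical power".

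For the arm comparison, the statistical analysis plan states: "A two-way mixed-design repeated-measures ANOVA will be used to assess" the effects of time, group and their interaction, with Tukey's test for between-group post hoc comparisons. It names no analysis set (intention-to-treat, modified or per-protocol), no missing-data method, no sensitivity analysis and no follow-up or analysis of eliminated participants.

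**The concern.** Missing a session and withdrawing are both things that happen after allocation, and either may depend on the technique received: painful sessions, lack of benefit, or early benefit. The arms differ by design in where the shocks are applied, and only the control arm is treated at the most painful palpated sites, so different tolerability between arms is plausible. If the people removed differ in outcome from those kept, and differ more in one arm than another, the remaining groups are no longer the ones that randomisation made comparable. An arm that loses its poor responders looks better than it is.

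The planned model adds to this. A standard repeated-measures ANOVA drops anyone without every analysed time point, so a participant who attends all three sessions but misses one later assessment would normally be lost too.

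Enlarging the sample does not help here. It restores precision but leaves selection bias where it was. If outcomes of eliminated participants are not collected, the bias cannot be examined afterwards.

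**Working it through.** **Inputs from the sample size calculation.** "Using a two-tailed α of 0.05, 80% power"; "an expected clinically relevant effect size of 2.0" (NPRS points); "a standard deviation of 2.1 (based on prior literature"; 17 evaluable per arm, 20% attrition, 23 per arm, 69 in total.

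**The plan's own figure.** n per arm = 2 × [2.1 × (1.960 + 0.842) / 2.0]² = 17.3, which rounds up to 18 against the stated 17. Allowing for attrition, 18 / 0.8 = 22.5, rounded up to 23, as stated. The sizing reproduces within one participant per arm and is not the problem.

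**Numbers at risk.** 20% of 69 = 13.8, about 14 people. Per arm, 23 × 0.8 = 18.4 remain.

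**Illustrative shift (assumption, not in the documents).** In one arm the removed 20% score 2 to 3 NPRS points worse than those kept; in the other arms loss is unrelated to outcome; there is no true difference.
- The mean of the full arm is 0.8 × kept + 0.2 × removed, so the kept mean differs from the full-arm mean by 0.20 × (2 to 3) = 0.4 to 0.6 points.
- Against the 2.0-point target this is 0.4 / 2.0 = 20% to 0.6 / 2.0 = 30%.

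**False-positive risk, one unadjusted two-sided comparison.**
- SE = 2.1 × √(2 / 18.4) = 0.69.
- Rejection probability = 1 − Φ(1.96 − shift/SE) + Φ(−1.96 − shift/SE).
- Shift 0.4: 0.089. Shift 0.6: 0.139. Without a shift: 0.05.

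**Under Tukey's test.** Simulation of three arms of 18, SD 2.1, one arm shifted, a single time point:
- Familywise error goes from 5% to about 8% (shift 0.4) and 13% (shift 0.6).
- Error for one comparison involving the shifted arm goes from about 2% to about 4% and 7%.

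**Other loss patterns.** Assume now that eliminated participants are 1 to 2 points worse than their arm's full mean. The completer mean shifts by d × gap / (1 − d), where d is the fraction lost. Error rates are for one unadjusted comparison.

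| Loss in the two arms | Bias (NPRS points) | False-positive risk |
|---|---|---|
| 20% and 20% | 0 | 5% |
| 20% and 0% | 0.25–0.50 | about 6.7%–11.9% |
| 10% and 30% | 0.32–0.63 | about 7.4%–14.9% |

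**Power if everyone is analysed as randomised.** With 23 per arm, suppose 20% do not attend fully and keep a fraction f of the effect. The difference is 2.0 × (0.8 + 0.2f). Noncentral t, SD 2.1, two-sided 5%:
- f = 1: difference 2.0, power 88%.
- f = 0.5: difference 1.8, power 81%.
- f = 0: difference 1.6, power 71%.

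For comparison, 18 completers per arm with a completer effect of 2.0 give 79%.

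**The case against.** A reader might infer that the plan prescribes a completers-only analysis and throws away data already collected. The documents do not say that. The elimination rule does not state whether an eliminated person leaves treatment, follow-up or the analysis, or what happens to earlier measurements. Complete-case deletion is a property of the standard ANOVA, not a sentence in the plan. This objection stands: the completers-only result is an inference, though the natural one from the rule, the model and the absence of any other provision.

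A reader might also attribute the whole 20% to the rule. The plan gives it as total anticipated attrition, not split by cause. A participant who withdraws consent for follow-up yields no further data under any wording. Only the part due to missed sessions, or to withdrawal from treatment alone, can be recovered.

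Nor is bias certain. All arms receive three weekly active sessions with the same number of shocks, the same stated intensity and nominal frequency, and the same home programme, and participants are to be blinded to technique. Strongly differential loss is therefore less obvious than in a sham-controlled trial. Equal loss of similar patients gives none. Participant blinding does not, however, stop discomfort or lack of benefit from driving absence, and the treatment site does differ between arms.

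Finally, the 9%–14% range is for one unadjusted comparison, which is not the planned test. Under Tukey's test the per-comparison risk is lower, but inflation remains.

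**Conclusion.** The concern holds in this form: the plan eliminates people for post-randomisation behaviour and offers no as-randomised analysis set or missing-data method, so a completers-only arm comparison is the likely outcome. This should be corrected, because it decides who enters the primary comparison.

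Confidence is high that the rule exists and that nothing in the plan offsets it. It is not high for the size or direction of bias, which the documents cannot supply. Under the stated adverse assumption the shift is 0.4 to 0.6 NPRS points, and false-positive risk rises from 5% to about 9%–14% (one unadjusted comparison) or about 8%–13% (familywise, Tukey, 18 per arm, treated as a single time point). Under equal, similar loss the bias is zero. A claim that the results will be biased by a given amount, or in favour of a given arm, would go beyond the documents.

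**What to change.** For analysis purposes, replace the elimination rule with: *all randomised participants are followed to four months where consent allows and analysed in their assigned arm, whatever the number of sessions attended.* This concerns follow-up and analysis only, not treatment.

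In the statistical analysis plan:
- Fit a mixed model for repeated measures by REML, using all available visits, and state its missing-data assumption. SPSS MIXED can fit it.
- Keep the three-session completers as a sensitivity analysis.
- Report missed sessions and withdrawals by arm, with reasons.

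The cost is more than rewording. The document is dated 4 September 2024, treatment is placed in July–September 2024, and recruitment is described in the past tense. Sessions may already have been missed, so the change needs a dated amendment and possibly re-contact of people already eliminated. On those same dates the four-month assessments were still to come. The estimated effect may be diluted by including non-attenders. On the assumptions above, power at 23 per arm stays at 81% or more if they keep at least half the effect, and falls to 71% only if they keep none.

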When the assumption of sphericity is violated, the Huynh–Feldt correction will be applied. Post hoc analyses will include:

- Bonferroni-adjusted pairwise comparisons for within-subject effects.
- Tukey's Honestly Significant Difference (HSD) test for between-group comparisons.

- Homogeneous subset analyses to identify clusters of similar treatment response profiles.

Effect size and power: Partial eta squared (η^2) will be reported to estimate the effect size. Observed power ($1-\beta$) will be documented where appropriate.

Statistical significance: A two-tailed p-value of ≤ 0.05 will be considered statistically significant for all analyses.

References

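### The stated 80% power names no test; for a specified Tukey pair, at one time point with SD 2.1, power is about 67% after the planned 20% attrition, and 17 and 23 per group do not agree

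*Combined protocol and SAP*

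**What the plan says.** In the Sample size calculation paragraph (Materials and methods), the trial is sized on pain intensity (NPRS): "Using a two-tailed α of 0.05, 80% power", "an expected clinically relevant effect size of 2.0" and an SD of 2.1 from earlier literature. From these, "the required sample size per group was 17 participants". The next step reads "Anticipating a 20% attrition rate, we adjusted the sample to 23 participants per group to preserve statistical power", which gives 69 over three arms. The paragraph names no test, no comparison and no allowance for multiplicity. It does not say whether the SD belongs to a raw or a change score.

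The Statistical analysis plan section specifies a mixed repeated-measures ANOVA with a three-level group factor. Its post hoc list assigns Tukey's "Honestly Significant Difference (HSD) test for between-group comparisons". The Bonferroni pairwise comparisons in that list are for within-subject effects, so Tukey is the only pairwise between-group test named.

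**The concern.** The four inputs are those of a two-group formula, but the trial has three arms and compares them in pairs with a multiplicity-adjusted test. A reader who sees 80% without qualification may take it to cover each technique against the pain-site-guided control. The title sets out that comparison, and Specific Objective 1 asks whether the application site matters. All three arms receive active radial pressure wave therapy, so small differences are plausible. A non-significant pair would then be weighed against a power figure that does not belong to that test. Separately, the 17 and the 23 in the same paragraph cannot both follow from a 20% loss.

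**Working it through.** **Inputs** (all from the Sample size calculation paragraph): difference 2.0, read as NPRS points because an SD stands beside it; SD 2.1; two-sided 0.05; 80% power; 17 per group; 20% attrition; 23 per group. The Tukey test comes from the post hoc list in the analysis plan.

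**1. The plan's 17, as one two-arm comparison.** n = 2(z₀.₉₇₅ + z₀.₈₀)²(SD/difference)² = 2 × (1.960 + 0.842)² × (2.1/2.0)² = 2 × 7.851 × 1.1025 = 17.31, which rounds up to 18. Normal-approximation power at 17 is 79.3%. By noncentral t it is 76.8% at 17, 79.3% at 18 and 81.5% at 19.

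**2. The plan's 17, as a three-group omnibus F.** The noncentrality is n × Σ(μᵢ − μ̄)²/SD².
- Means 0, 0, 2: the sum of squares is 2.667, so 17 × 2.667/4.41 = 10.28. Power is 80.1% at 17 and 77.3% at 16, so 17 is the smallest size that reaches 80%.
- Means 0, 1, 2: the sum of squares is 2, so 17 × 2/4.41 = 7.71. Power is 67.1% at 17.

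**3. A specified Tukey pair.** Reject if |t| exceeds q(0.95; 3, 3n − 3)/√2. The noncentrality is 2.0/(2.1 × √(2/n)), for one time point.

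| Per arm | Situation | Noncentrality | Tukey critical t | Unadjusted two-sample t | Specified Tukey pair |
|---|---|---|---|---|---|
| 17 | stated requirement | 2.777 | 2.418 | 76.8% | 64.1% |
| 18 | 23 less 20% | 2.857 | 2.414 | 79.3% | 67.1% |
| 23 | no loss | 3.230 | 2.398 | 88.5% | 79.5% |

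A simulation of 200,000 trials gives 64.2% at 17 and about 67% at 18. The nominal two-sided level per pair is about 0.019. Part of the fall from 80% to 64% comes only from moving from normal to t quantiles. On the t basis, Tukey lowers power at 17 from 77% to 64%.

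**4. At least one significant Tukey pair** (same simulation). With one arm 2.0 from two equal arms: 79% at 17 and 82% at 18. With evenly spaced means: 67% at 17 and 70% at 18.

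**5. Attrition.** 17/0.8 = 21.25, so 22. The cruder 17 × 1.2 = 20.4 gives 21. Neither is 23, but 18/0.8 = 22.5 does give 23. In the other direction, 23 × 0.8 = 18.4, so 18 are expected to remain.

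**6. Dependence on the within-person correlation.** The documents give none, so 0.3, 0.5 and 0.7 are assumptions.
- Baseline-adjusted four-month comparison with Tukey, residual SD 2.1 × √(1 − ρ²), 18 per arm: 72%, 81% and 94%.
- Tukey on means averaged over baseline and two follow-ups, with no baseline difference and 2.0 at both follow-ups, so an averaged difference of 4/3 and SD 2.1 × √((1 + 2ρ)/3), 17 per arm: 55%, 45% and 37%.
- If 2.1 is already a change-score SD, the figures in step 3 apply to the change score.

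**The case against.** The strongest reply is that the trial was sized for the overall group effect. An ANOVA with a three-level group factor is the planned model, the omnibus F with one arm apart gives exactly 17, and leaving post hoc pairs at lower power is a common choice. This stands in part. A reader might infer that 17 is simply an arithmetic error for 18. The documents do not support that, because they do not say which test was used and one reasonable test gives 17. But they do not state the omnibus test or the favourable configuration either, evenly spaced means give only 67.1%, and a significant F does not say which technique differs.

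A reader might also infer that a wholly null trial would miss a real difference one time in three. That is too strong. If one arm differs from both others, Tukey flags at least one pair 79% to 82% of the time, a miss rate of about one in five. One in three applies to a named pair, or to evenly spaced means.

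It is equally tempting to call 64% or 67% the power of the planned analysis. These are single-time-point figures with SD 2.1. Power in the repeated-measures model depends on a correlation and an SD definition that the plan does not give, and step 6 shows that it could be higher or lower.

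Finally, 23 per arm is one more than 17/0.8 requires, so the attrition slip errs on the safe side, and with no losses a Tukey pair would have 79.5%. That is true, but the plan itself expects 20% loss, and its elimination criteria remove anyone who misses a session.

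**Conclusion.** The section is wrong as written, in two limited respects. First, the unqualified 80% does not hold for a specified pair under the only pairwise between-group test in the plan once the plan's own attrition occurs: power is about 67% at 18 per arm, assuming a 2.0-point difference, SD 2.1 and one time point. Second, 17 and 23 are inconsistent under a 20% loss. The paragraph does not promise 80% for every pair, so these figures do not show that the trial needs more participants. They show that the claim must be tied to a test and a comparison before a non-significant result can be read against it.

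**What to change.** Keep 69 participants and restate the paragraph:
- Name the test and comparison to which the 80% refers. If it was the omnibus F, state the configuration of means, and give 67.1% for evenly spaced means.
- State that 2.0 is in NPRS points, and whether SD 2.1 is for a raw or a change score.
- Give 18 per arm for one unadjusted two-arm comparison (19 by t-test), and show 18/0.8 = 22.5, rounded up to 23.
- Report power of about 67% for a specified Tukey pair after 20% loss, with its single-time-point assumption.
- If a baseline-adjusted four-month comparison is adopted instead, fix it before any group comparison is seen. Report 72%, 81% or 94% for correlations of 0.3, 0.5 or 0.7, marked as assumptions.

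The cost is rewording, with no extra participants. The downside is that the stated power becomes less favourable. The baseline-adjusted option would also change the planned analysis, and its gain rests on a correlation that the documents do not supply.
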